**PRIOR/CONCOMITANT THERAPY**

8. Past or intended use of over-the-counter or prescription medication, including herbal medications, NSAIDs, PPIs or anti-H2 antagonists within 7 days (or 14 days if the drug is a potential enzyme inducer) or 5 half-lives (whichever is the longest) prior to dosing. Other concomitant medication may be considered on a case by case basis by the investigator in consultation with the medical monitor.

**PRIOR/CONCURRENT CLINICAL STUDY EXPERIENCE**

9. Participation in the study would result in loss of blood or blood products in excess of 500 mL within a 56-day period.
10. Exposure to more than 4 new chemical entities within 12 months prior to the first dosing day.
11. The subject has participated in a clinical trial and has received an investigational product within the following time period prior to the first dosing day in the current study: 30 days, 5 half-lives or twice the duration of the biological effect of the investigational product (whichever is longer).
12. Sensitivity to any of the study treatments, or components thereof, or drug or other allergy that, in the opinion of the Investigator or GSK Medical Monitor, contraindicates participation in the study.
13. Regular use of known drugs of abuse.

**DIAGNOSTIC ASSESSMENTS AND OTHER CRITERIA**

14. Subjects with renal function defined as Chronic Kidney Disease Epidemiology Collaboration (CKD-EPI) with an age appropriate GFR  $\leq 90$  (ml/min/1.73m^2).
15. Presence of Hepatitis B surface antigen (HBsAg) or Positive Hepatitis C antibody test result at screening.
16. Positive human immunodeficiency virus (HIV) antibody test.
17. Positive pre-study drug/alcohol screen.
18. Presence of clinically significant haematuria and/or proteinuria.

19. Carbon monoxide levels indicative of smoking or history or regular use of tobacco- or nicotine-containing products within 3 months prior to screening.
20. Abnormally low blood pressure as determined by the Principal Investigator
21. **Part A (Food Effect) Cohort 3 only:** Participant must have no dietary restrictions (e.g., lactose intolerance) or inability to eat an adapted standard meal (includes 35-40% fat content).
22. **Part A (Food Effect) Cohort 3 only:** History of gall bladder surgery or gall bladder removal, or history of an acute disease state (e.g. cholelithiasis) within 14 days prior to receiving the study treatment.
23. **Part B only:** Early morning cortisol < 420 nmol/L and inadequate response (rise of <250mmol/L from baseline) to ACTH stimulation test at Day -1.

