## 2.2. PART B (Cohorts 4-6)

Procedure	Screening (Up to 28 days before Day 1)	Study Period (Days)													Follow-up (14-21 days post last dose) / Early Withdrawal	Notes	
		-2	-1	1	2	3	4	5	6	7	8	9	10	11	12		
Outpatient Visit	X															X	
Admission to Clinical Unit		X															
Inpatient Stay at Clinical Unit			←-----X-----→														
Discharge from Clinical Unit																X	Following completion of all assessments.
Informed Consent	X																
Inclusion and Exclusion Criteria	X																
Demography	X																
Full Physical Examination	X																Additional exams/screens may be performed, or brief exams can be made into full exams, by the Investigator, as deemed necessary (e.g. where safety or laboratory findings indicate). Tests will be conducted within site specified standards.
Brief Physical Examination			X	X				X					X	X			
Drug/Alcohol/Smoki ng Screen	X		X														Tests include alcohol breath test, smoking breath test and urine drug screen.
Medical/Medication/ Drug/Alcohol History	X																
HIV, Hepatitis B and C Screening	X																
FSH + Oestradiol	X																Females only, if required
Holter Monitoring (48 hour)	X																

Procedure	Screening (Up to 28 days before Day 1)	Study Period (Days)													Follow-up (14-21 days post last dose) / Early Withdrawal	Notes		
		-2	-1	1	2	3	4	5	6	7	8	9	10	11	12	13		
Haematology/ Clinical Chemistry /Urinalysis Test	X		X		X		X		X		X		X		X		X	If trace protein is detected, a repeat test can be performed.  Sample to be drawn pre-dose on Days 2, 4, 6, 8 and 10.  Non-fasted samples can be collected on Day -1 and Follow-Up Visit. All other samples to be collected in fasted state.
Cortisol Test			X											X			Tests to be performed in the early morning on Day -1 and Day 11. If levels are <420 nmol/L, then a adrenocorticotropic hormone (ACTH) stimulation test will be performed to assess hypothalamic pituitary adrenal (HPA) axis.	
Safety biomarkers (KIM1, NGAL, Urinary albumin)				X				X									First urine sample of the morning to be collected (pre-dose). Additional samples may be collected, as deemed necessary by the Investigator (e.g. where safety or laboratory findings indicate).	
Telemetry				X	X												Continuous at least 24 hr post-evening dose. Initiate at least 15 min. prior to dosing.	
Randomization				X														

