	
for 7 days (mean AUC 204 µg.h/mL on Day 7).
 
 
• This test article-related, non-adverse finding correlated with increased adrenal weight following 28 days dosing in male rats given ≥100 mg/kg/day, as SDD, and female rats given ≥25 mg/kg/day, as SDD.
 
	
Therefore, no specific monitoring, other than standard clinical and laboratory parameters, will be implemented for healthy volunteers during SAD part of the study. However, for the MAD cohorts, adrenal function will be assessed prior to first dose and on completion of 10 days dosing. Also, by observing the safety margin for renal findings of up to 3-fold (during the SAD part of the study) and up to 5-fold (during the MAD part of the study) for the total daily AUC and <math>C_{max}</math> to be below the female rat NOAEL (AUC: 434 µg.h/mL, <math>C_{max}</math>: 46.2 µg/mL), should reduce the risk of adrenal and ovary effects in humans.
 
Exclusion criteria (Part B only):
 
 
• Participants with borderline adrenal glucocorticoid function (early morning serum cortisol < 420nmol/L) will only be included in the study if after an adrenocorticotropic hormone (ACTH) stimulation test, there is a rise in cortisol level from baseline of at least 250nmol/L
 
 
Monitoring:
 
 
• Participants will be monitored clinically for any symptoms of adrenal insufficiency, (nausea, vomiting, dizziness) and objective assessments (supine/standing BP). Depending on the investigators clinical judgement, a ACTH
 

Potential Risk of Clinical Significance	Summary of Data / Rationale for Risk	Mitigation Strategy
		
stimulation test may be done to exclude adrenal insufficiency.
 
Day 11 (Part B only):
 
 
• Early morning serum cortisol (+ ACTH stimulation test if levels < 420nmol/L) will be performed on all participants at Day 11. If during Day 11 early morning cortisol is < 420 nmol/L, volunteers will undergo a ACTH stimulation test the next day to rule out adrenal insufficiency. Participants with adrenal insufficiency will be withdrawn from the study, refer to Section 8.1.4.
 
 
Stopping criteria:
 
 
• A stopping criterion has been included if one or more volunteers in Part B develop adrenal insufficiency with clinical signs and symptoms.
 

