## 6. STUDY POPULATION

Prospective approval of protocol deviations to recruitment and enrolment criteria, also known as protocol waivers or exemptions, is not permitted.

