### 8.1.4. Adrenal Withdrawal Criteria (Part B only)

- A participant that develops adrenal insufficiency will be withdrawn from the study. Adrenal insufficiency is defined by an early morning serum cortisol < 420 nmol/L and following an ACTH stimulation test, serum cortisol does not rise by >250 nmol/L from baseline. Any case of adrenal insufficiency will be referred to an endocrinologist for confirmation.

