4.1. Protocol Deviations

Important protocol deviations (PDs), including deviations related to study inclusion/exclusion criteria, conduct of the trial, patient management or patient assessment) will be summarised and listed.

Protocol deviations will be tracked by the study team throughout the conduct of the study in accordance with the Protocol Deviation Management Plan [Version 1.0 dated 10 April 2019 or later].

Exclusion from the analysis sets due to a deviation will be determined programmatically using the criteria described in the table of Analysis populations above. These deviations will not be included in the SDTM dataset but will be programmed in the protocol deviation analysis (ADaM) dataset. This dataset will be the basis for the summaries and listings of protocol deviations.

Data will be reviewed prior to unblinding and freezing the database to ensure all important deviations and deviations which may lead to exclusion from the analysis are captured and categorised.

A separate summary and listing of all inclusion/exclusion criteria deviations will also be provided. This summary will be based on data as recorded on the inclusion/exclusion page of the eCRF.

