10. APPENDICES

10.1. Appendix 1: Protocol Deviation Management and Definitions for Per Protocol Population

10.1.1. Exclusions from Analysis Population

Per protocol population is not defined in this protocol.

Important protocol deviations and violations of the inclusion and exclusion criteria will be listed.

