10.2.2. Protocol Defined Schedule of Events in PART B (Cohorts 4-6)

Procedure	Screening (Up to 28 days before Day 1)	Study Period (Days)													Follow-up (14-21 days post last dose) / Early Withdrawal	Notes	
		-2	-1	1	2	3	4	5	6	7	8	9	10	11	12		
Outpatient Visit	X															X	
Admission to Clinical Unit		X															
Inpatient Stay at Clinical Unit				←=====X=====→													
Discharge from Clinical Unit																X	Following completion of all assessments.
Informed Consent	X																
Inclusion and Exclusion Criteria	X																
Demography	X																
Full Physical Examination	X																Additional exams/screens may be performed, or brief exams made full exams, by the Investigator, as deemed necessary (e.g. where safety or laboratory findings indicate). Tests will be conducted within site specified standards.
Brief Physical Examination			X	X				X					X	X			
Drug/Alcohol/Smoki ng Screen	X		X														Tests include alcohol breath test, smoking breath test and urine drug screen.
Medical/Medication/ Drug/Alcohol History	X																
HIV, Hepatitis B and C Screening	X																
FSH + Oestradiol	X																Females only, if required
Holter Monitoring (48 hour)	X																

Procedure	Screening (Up to 28 days before Day 1)	Study Period (Days)													Follow-up (14-21 days post last dose) / Early Withdrawal	Notes	
		-2	-1	1	2	3	4	5	6	7	8	9	10	11	12		
Haem/Chem/ Urinalysis Test (Include Liver Chemistries)	X		X		X		X		X		X		X		X	X	If trace protein is detected, a repeat test can be performed. Sample to be drawn pre-dose on Days 2, 4, 6, 8 and 10. Non-fasted samples can be collected on Day -1 and Follow-Up Visit. All other samples to be collected in fasted state.
Cortisol Test			X										X				Tests to be performed in the early morning on Day -1 and Day 11. If levels are <420 nmol/L, then a ACTH stimulation test will be performed to assess hypothalamic pituitary adrenal (HPA) axis.
Safety biomarkers (KIM1, NGAL, Urinary albumin)				X				X									First urine sample of the morning to be collected (pre-dose). Additional samples may be collected, as deemed necessary by the Investigator (e.g. where safety or laboratory findings indicate).
Telemetry				X	X												Continuous at least 24 hr post-evening dose. Initiate at least 15 min. prior to dosing.
Randomization				X													

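### Exclusion criterion 23 gives the ACTH cortisol-rise threshold in mmol/L where the rest of the protocol uses nmol/L

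*Protocol*

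**What the plan says.** Exclusion criterion 23 (Protocol 6.2, Part B only) has two parts. The candidate's early morning cortisol is below 420 nmol/L, and the ACTH stimulation test on Day -1 gives an "inadequate response (rise of <250mmol/L from baseline". The first limit is in nmol/L and the second in mmol/L.

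The adrenal row of the risk table in Protocol 3.3.1 states the same entry rule the other way round. A participant with borderline cortisol enters only if, after ACTH, "there is a rise in cortisol level from baseline of at least 250nmol/L".

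Protocol 8.1.4 uses the same quantity for withdrawal. Adrenal insufficiency means a morning cortisol below 420 nmol/L where, after ACTH, "serum cortisol does not rise by >250 nmol/L from baseline".

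The Part B schedule (Protocol 2.2) sets the trigger for the test: "If levels are <420 nmol/L, then a adrenocorticotropic hormone (ACTH) stimulation test will be performed". SAP 10.2.2 repeats that trigger in nmol/L and does not restate the rise.

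On how strictly criteria apply, Protocol 6 says: "Prospective approval of protocol deviations to recruitment and enrolment criteria, also known as protocol waivers or exemptions, is not permitted".

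**The concern.** One sentence gives two limits for the same analyte in units a million-fold apart, and two other sections contradict the second limit. This is the criterion a site applies to decide who enters Part B, not background text.

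For a candidate with cortisol below 420 nmol/L who responds adequately to ACTH, the wording of exclusion 23 says exclude and 3.3.1 says admit. Under the literal wording the entry ACTH test also has no function, because its result cannot change the decision. With waivers ruled out, a site that follows 3.3.1 enrols someone whom the text of exclusion 23 excludes.

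The criterion guards one of the organ risks named in 3.3.1. Under 8.1.2, a single Part B participant who meets the adrenal withdrawal rule with compatible signs or symptoms stops dosing. The entry threshold for that risk should be stated correctly.

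**Working it through.** No sample-size or power figure is involved. The check is a comparison of texts and a unit conversion.

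**1. The three statements of the required rise**

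| Place | Use | Threshold for the rise |
|---|---|---|
| Protocol 3.3.1, adrenal row | Entry to Part B | at least 250 nmol/L admits |
| Protocol 6.2, exclusion 23 | Entry to Part B | <250 mmol/L excludes |
| Protocol 8.1.4 | Withdrawal | not >250 nmol/L is insufficiency |

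Two of the three are in nmol/L. The odd one out is the exclusion criterion itself.

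**2. All numeric cortisol thresholds in the two documents**

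| Place | Thresholds | In nmol/L | In mmol/L |
|---|---|---|---|
| Protocol 2.2, cortisol test | 1 | 1 | 0 |
| Protocol 3.3.1, adrenal row | 4 | 4 | 0 |
| Protocol 6.2, exclusion 23 | 2 | 1 | 1 |
| Protocol 8.1.4 | 2 | 2 | 0 |
| SAP 10.2.2, cortisol test | 1 | 1 | 0 |
| Total | 10 | 9 | 1 |

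**3. Size of the discrepancy**

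- 1 mmol/L = 10^6 nmol/L, so 250 mmol/L = 250 × 10^6 = 250,000,000 nmol/L.
- Against the threshold in 3.3.1 and 8.1.4: 250,000,000 / 250 = 10^6.
- Against the morning cutoff in the same sentence: 250,000,000 / 420 ≈ 595,000.

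No cortisol rise could reach that value. Every response would count as inadequate, and the criterion would reduce to excluding anyone with morning cortisol below 420 nmol/L.

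**4. Is the text current?** The summary of changes for Amendment 1 lists two changes to the exclusion criteria, on renal function and on low blood pressure. Exclusion 23 is not among them, so the mmol/L wording is in force.

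**5. Reach into the analysis.** The populations in SAP 4 rest on screening, randomization, dosing and PK data. SAP 10.1.1 states: "Per protocol population is not defined in this protocol". For the separate summary of eligibility deviations, SAP 4.1 says: "This summary will be based on data as recorded on the inclusion/exclusion page of the eCRF". The threshold therefore enters no derivation and defines no analysis set.

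**6. Check of the corrected value.** With 250 nmol/L, exclusion 23 removes rises below 250 and 3.3.1 admits rises of at least 250. The two are then exact complements.

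**The case against.** The strongest reply is that nobody would be misled. The same sentence gives basal cortisol in nmol/L, 3.3.1 spells out the same rule with the right unit, and a threshold no result could meet identifies itself as a slip. Applying the rule as 3.3.1 states it is consistent reading, not a waiver. Even a literal application could only turn away borderline candidates; it could not admit anyone with adrenal insufficiency. Day 11 monitoring and withdrawal use nmol/L throughout. The factor of 10^6 measures the unit prefix, not an effect on the trial.

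Most of this stands, and it is why the point is minor. It limits the consequence without making the text right: a site should not have to correct an eligibility threshold by inference.

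A second reply is that the point turns on one letter, and exclusion 23 appears only once, so no second copy confirms it. A misreading of that character in the electronic text cannot be fully excluded, although the 420 limit in the same criterion reads correctly as nmol/L. A look at the sponsor's master copy settles it.

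**Conclusion.** The unit in exclusion 23 is wrong as written, and the intended value, 250 nmol/L, is clear from 3.3.1 and 8.1.4. The error is a factor of 10^6 in one decision threshold. Its practical effect is small: it concerns only Part B candidates with Day -1 cortisol below 420 nmol/L, and the literal reading over-excludes rather than under-protects. Part B plans 3 cohorts × 8 = 24 participants. The documents do not say how many candidates would fall below 420 nmol/L, so the number affected cannot be given. Sample size, endpoints and analysis populations are untouched.

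This rests on one assumption: that the master copy of the protocol reads mmol/L, as the text available here does.

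**What to change.** In exclusion criterion 23, replace mmol/L with nmol/L for the cortisol rise. That is one letter, to be made at the next amendment after a look at the master copy. Design, data collection and analysis do not change.

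A separate, optional tidy-up concerns the boundary. A rise of exactly 250 nmol/L passes at entry under 3.3.1 but counts as insufficiency under 8.1.4, which requires more than 250. If the sponsor wants the same convention at entry and at Day 11, 8.1.4 can define insufficiency as a rise of less than 250 nmol/L. That costs one further phrase, and the main correction does not depend on it.

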### **6.3. Lifestyle Considerations**

#### **6.3.1. Meals and Dietary Restrictions**

- Refrain from consumption of red wine, Seville oranges, grapefruit or grapefruit juice, pomelos, exotic citrus fruits, grapefruit hybrids, or fruit juices from 7 days prior to each first dose of study treatment in Part A up until discharge from the unit. In Part B, participants must refrain from consumption of red wine, Seville oranges, grapefruit or grapefruit juice, pomelos, exotic citrus fruits, grapefruit hybrids, or fruit juices from 7 days prior to the first dose of study treatment until after the final dose.
- For cohort 3 of Part A, after an overnight fast of at least 8 hours, participants should start eating their breakfast 30 minutes prior to the dose of study drug and should consume the entire breakfast within 25 minutes. The study drug should be administered within 5 minutes of the completion of the meal. Participants will receive an adapted standard breakfast. 8 fl oz (240ml) of water is to be taken at the time of dosing. Water is allowed ad libitum up to 1 hour before dosing and from 1 hour after dosing.

#### **6.3.2. Caffeine, Alcohol, and Tobacco**

- During each dosing session, participants will abstain from ingesting caffeine- or xanthine-containing products (e.g., coffee, tea, cola drinks, and chocolate) for 24 hours before the start of dosing until after collection of the final PK sample.
- During each dosing session, participants will abstain from alcohol for 24 hours before the start of dosing until after collection of the final PK sample.
- Use of tobacco products will not be allowed from 3 months prior to screening until after the final follow-up visit.

### **6.3.3. Activity and Travel**

- Participants will abstain from strenuous exercise for 48 hours before each blood collection for clinical laboratory tests. Participants may participate in light recreational activities during studies (e.g., watching television, reading).
- Participants must not have travelled to an area (as determined by the investigator) with a high prevalence of leishmanial/parasitic infections in the 6 months before screening or intend to do so in the 3 months after the final dose of study treatment.

### **6.4. Screen Failures**

Screen failures are defined as participants who consent to participate in the clinical study but are not subsequently randomized. A minimal set of screen failure information is required to ensure transparent reporting of screen failure participants to meet the Consolidated Standards of Reporting Trials (CONSORT) publishing requirements and to respond to queries from regulatory authorities. Minimal information includes demography, screen failure details, eligibility criteria, and any serious adverse events (SAEs).

Individuals who do not meet the criteria for participation in this study (screen failure) may be rescreened at the discretion of the Principal Investigator, and Medical Monitor if required. Rescreened participants should be assigned a new participant number.

## **7. STUDY TREATMENT**

Study treatment is defined as any investigational treatment(s), marketed product(s), placebo, or medical device(s) intended to be administered to a study participant according to the study protocol.

## 7.1. Study Treatment(s) Administered

	Study Treatment	
Product name:	GSK3186899	Placebo
Formulation description	Spray dried powder	Blend
Dosage form:	Powder in bottle (Extemporaneous Compounding)	Powder in bottle (Extemporaneous Compounding)
Unit dose strength(s)/Dosage level(s):	full dose per bottle	NA
Route of administration:	For oral use only	For oral use only
Dosing instructions:	Suspend in diluent and dose.	Suspend in diluent and dose.
Physical description:	White to slightly coloured powder	White to slightly coloured powder
Diluent description:	A mixture of propylene glycol and water	A mixture of propylene glycol and water
Source of procurement	Study medication is supplied by GlaxoSmithKline	Study medication is supplied by GlaxoSmithKline
Method for individualizing dosage:	Site to assemble	Site to assemble

## 7.2. Preparation/Handling/Storage/Accountability

- The investigator or designee must confirm appropriate temperature conditions have been maintained during transit for all study treatment received and any discrepancies are reported and resolved before use of the study treatment.
- Only participants enrolled in the study may receive study treatment and only authorized site staff may supply or administer study treatment. Only unblinded pharmacy site staff (or designees) may prepare the study treatment. All study treatments must be stored in a secure, environmentally controlled, and monitored (manual or automated) area in accordance with the labeled storage conditions with access limited to the investigator and authorized site staff.
- The investigator, institution, or the head of the medical institution (where applicable) is responsible for study treatment accountability, reconciliation, and record maintenance (i.e., receipt, reconciliation, and final disposition records).
- Further guidance and information for the final disposition of unused study treatment are provided in the SRM.
- Under normal conditions of handling and administration, study treatment is not expected to pose significant safety risks to site staff.
- A Material Safety Data Sheet (MSDS)/equivalent document describing occupational hazards and recommended handling precautions either will be provided to the investigator, where this is required by local laws, or is available upon request from GSK.

